PeerFIT Intervention: The 12-month PeerFIT intervention consists of a 6-month intensive phase including: (a) once weekly 90-minute group weight management and exercise session led by a lifestyle coach; (b) once weekly one-hour physical activity session delivered in community settings; and (c) Facebook and mHealth technology (i.e., Fitbits, text messaging support) to increase motivation and facilitate self-monitoring and peer social support for health behavior change. Participants then transition to a 6-month lower intensity phase in which the 90-minute weight management sessions are discontinued. During the low intensity phase, participants will have continued access to the physical activity sessions, social media, and mHealth support described below. A total of 10-18 participants will be enrolled in each of the in-person groups with participants from all groups invited to join the secret PeerFIT Facebook group. The groups will be conducted as open groups with a minimum of 2 and maximum of 18 participants at any given time to offer more diversity and perspective from peer members. After 2 participants are enrolled, each new participant who joins the group will receive an orientation called the “Start Up Session” prior to the group session. The orientation session will be done individually or in a small group setting. The orientation session will last about one hour and will be conducted within one week prior to joining an existing PeerFIT group when possible.

Weight Management and Exercise Sessions. The PeerFIT weight management and physical activity component is adapted from the evidence-based Diabetes Prevention Program designed for individuals at risk for diabetes and cardiovascular disease in the general population. PeerFIT goals are to achieve 5% weight reduction and to increase physical activity gradually to 150 minutes per week over a 6-month period. A private and confidential weigh-in is conducted at the beginning of each session to track participants’ progress. Participants are taught to achieve their weight loss and fitness goals by lowering calorie intake by reducing their consumption of sugar-sweetened beverages and junk foods that are high in sugar and fat and eating fewer processed foods, while adding more fruits and vegetables and lean protein into their diets, and by

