Comparison Condition: Basic Education supported by wearable Activity Tracking (BEAT)

Participants in the comparison condition will receive monthly individual lifestyle sessions delivered by a lifestyle coach including education, guidance, and support for self-monitoring behaviors (i.e., daily self-weighing and tracking daily steps) during the first six months of the study, plus text message reminders and encouragement for self-monitoring weight loss behaviors (3-5 text messages per week) during the entire 12-month study period. During the initial session, information about psychiatric medications and health behaviors associated with obesity in young adults with mental illness are presented as well as information about the role of healthy eating and exercise in improving physical health and mental health outcomes. Self-monitoring behaviors including daily self-weighing and physical activity monitoring are introduced as strategies for weight loss and increasing cardiovascular fitness. Participants will receive materials with tips and strategies for healthy eating and increasing physical activity. They will also be given a wearable activity tracker (i.e., Fitbit Zip, Flex 2, or Inspire) to use throughout the study with instructions for using the device and connecting it with their personal smartphone, tablet, or computer. The Fitbit Zip and Inspire are equipped with an LCD display that can be used to observe daily step counts without connecting to a smartphone or computer if participants do not own one. The Fitbit Flex 2 indicates progress towards step goals with LCD lights that light up on the wrist band, and more data such as exact steps can be monitored through the Fitbit app on participants' phones. Participants in the comparison condition will also receive routine access to technical assistance for using the Fitbit during the

monthly lifestyle sessions. The lifestyle coach providing the sessions will make sure the Fitbit is working properly, answer any questions about the device, and show participants how to check their progress by synching the Fitbit to a personal computer or smartphone. Participants may contact the lifestyle coach during business hours for one-on-one phone based technical assistance for using the device, but no active assistance is provided during these telephone contacts for behavioral strategies for weight loss.

Study Sites.

Mental Health Center of Greater Manchester (MHCGM)

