Bay Cove Human Services (Bay Cove) and Lindemann Mental Health Center (LMHC) are CMHCs providing comprehensive outpatient mental health services to people with SMI in the Metro-Boston area. Participants enrolled from this site will be supervised by Vinfen Project Manager, [name].

Study Participants

Research staff (employees of the Vinfen organization, MHCGM, GNMHCCC, CMHA, and Dartmouth) will complete a brief pre-screen with potential participants in person or over the telephone. The pre-screen will ask participants to self-report whether they meet the age criteria (18 to 35 years old) and psychiatric diagnosis criteria (chart diagnosis of SMI using diagnostic criteria as defined in the DSM-V for schizophrenia and psychotic disorders, mood disorders, anxiety disorders, and borderline personality disorder) for the study. In addition, participants will be asked to indicate whether they are interested in working on weight loss and fitness goals. If the participant meets the initial eligibility criteria based on the pre-screen, they will be invited to attend a screening session during which the study inclusion and exclusion criteria will be reviewed. Participants will be asked to give written consent to participate in the screening session by signing an information sheet. In addition, they will be asked to complete a two-way authorization form giving permission for the research staff to review their medical records to verify their psychiatric diagnosis.

Inclusion criteria	Note: All of the following inclusion criteria must be met at the time of written consent to enroll in the study
Demographics	
▪ Male, female, or transgender (no exclusion criteria based on gender or sexual orientation)▪ Ages 18 to 35 years old▪ Any race or ethnicity▪ English speaking
Mental health diagnosis	
▪ MA DMH, MHCGM, GNMHCCC, or CMHA client with a qualifying chart diagnosis of SMI using diagnostic criteria as defined in the DSM-V for

	schizophrenia and psychotic disorders, mood disorders, anxiety disorders, and borderline personality disorder
Body mass index	
 Overweight, defined by Body Mass Index at least 25.0 kg/m²
Informed consent	
 Able and willing to give written informed consent to participate in the study or able to assent with guardian consent

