Psychiatric Medications	
 Client must not have started (discontinuation and dose changes OK) the psychiatric medications olanzapine or clozapine in the last two months based on self-report.
Medical clearance	
 If screening indicates CVD risk, diabetes, a positive PAR-Q screening, or angina, able and willing to obtain a medical clearance letter from a primary care provider prior to enrolling in the study.
Program Participation	
 Willingness to be randomized to either of the two conditions Able and willing to attend the weekly 90-minute weight management session, participate in the weekly 1-hour physical activity sessions, and use the Facebook and mHealth (i.e., Fitbits and text messaging) components of the PeerFIT program

Exclusion criteria	
Contraindication to weight loss	
 Self-report of any of the following medical conditions will require medical clearance by a primary care provider to participate in the study: 
 -Heart condition -History of anorexia nervosa -Past diagnosis of or treatment for anorexia nervosa or bulimia nervosa -Cardiac event within the past 6 months, for example: 
 -Arrhythmias -Heart valve disease -Cardiomyopathy (enlarged heart) -Carotid or coronary artery disease Self-report of any of the following medical conditions will result in exclusion from participating in the study: 
 -Liver failure -Cancer requiring active treatment (except for non-melanoma skin cancers) -Chronic use of steroid medication -Unable to walk for physical activity -History of weight loss surgery or planning weight loss surgery during study period -5% or greater weight loss in 3 months prior to screening session as indicated by self-report -Pregnant, breastfeeding, or planning a pregnancy during study period because reduction in calorie intake may be contraindicated
Substance Use	
 Active substance use, with the exception of marijuana/synthetic cannabinoids, determined to be incompatible with participation in the intervention identified by screening questionnaire that assesses for excessive use according to intake limits by gender Use of anabolic steroids with the drug taken at least "most days of the week for the previous month"
Stroke	
 History or stroke

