- 5) Review self-report of psychiatric medications over the past two months by reviewing a medication list with the participant.
- 6) Assess current ability to walk for physical activity.
- 7) Assess transportation to attend study activities.
- 8) Confirm willingness to be randomized and participate in either PeerFIT or BEAT.
- 9) Confirm willingness to participate in weekly activities if randomized to PeerFIT.
- 10) Discuss any plans of moving out of catchment area in the next 12 months.
- 11) Discuss upcoming surgeries that would prevent participation.
- 12) Assess for any scheduling conflicts that would prevent participating in study activities.
- 13) Discuss with client his/her current participation in other lifestyle programs with a focus on weight loss and fitness (e.g., InSHAPE, Weight Watchers)
- 14) Assess pregnancy, plans for pregnancy, or breastfeeding.
- 15) Assess for frequent use ("most days of the week for the previous month") of anabolic steroids to build muscles.
- 16) Assess for any past or planned weight loss surgery.
- 17) Determine whether participant has lost 5% or more weight loss in the last 3 months.
- 18) Assess any speaking, major visual, or hearing impairments that could interfere with ability to participate.
- 19) Use Mini Mental Status Examination to determine whether client has cognitive impairment sufficient to interfere with their ability to provide informed consent, complete study questionnaires, or participate in a group intervention as indicated by a MMSE score equal to or greater than 24.
- 20) Current alcohol and substance use will be assessed with a series of screening questions assessing use over the past month
- 21) Assess for present or history of anorexia nervosa or bulimia nervosa
- 22) In addition, we will use the PAR-Q²⁰—a widely used physical activity appraisal questionnaire—and a

medical condition checklist to assess contraindications to participating in a moderate intensity exercise program. The intervention emphasizes the achievement of moderate, not vigorous intensity physical activity; the safety of moderate intensity physical activity in subjects with no prior cardiac event and no anginal symptoms is well established. If potential participants screen positive to any of the PAR-Q items, a prior history of cardiovascular disease, cardiac event, or have diabetes mellitus, they will need a signed approval letter from their primary care provider.

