The screening process will cease if a potential participant fails to meet any of the inclusion criteria listed above. Similarly, if a potential participant meets any of the exclusion criteria listed above the screening will be stopped and the participant will be deemed ineligible for the study. If an approval letter from the primary care provider is needed, all other questions in the screener will be completed and the screening session will be tracked as “pending” until clearance is obtained. It will also be tracked as “pending” in instances where based on a participant’s response, it is not clear if he/she meets study criteria, and the study team member must review the case with the study team to determine eligibility.

Verbal Consent for Modification to Interview Format

In the case that an assessment will be conducted over the phone due to social and physical distancing restrictions verbal consent will be collected prior to the interview. A study staff member will contact the participant by phone up to two weeks before the assessment is due and read the Information Sheet to the participant. During this time the study staff member will be able to address any questions or concerns the participant has about the phone-based interview. Staff will confirm the participant can be available for up to two hours for the interview and has access to a reliable phone for this amount of time. Once the participant has given verbal consent to conduct the interview, the study staff and participant will work together to schedule the phone interview at a time that is mutually convenient.

DATA COLLECTION AND MEASUREMENT

Data Collection for Aims 1 and 2

Trained research interviewers blind to group assignment will administer research assessments that include primary outcome data to consented participants at baseline, and at 6 and 12 months after randomization. Participants will receive \$50 or receive a \$50 gift card of their choice for completing each of the primary assessments at baseline, 6-and 12 months, for a total of \$150. In addition, at 6 and 12 months, an unblinded research interviewer will conduct a brief 30-minute telephone assessment with PeerFIT participants to collect data on secondary measures specific to the experimental condition. PeerFIT participants will be paid an additional \$15 or given a \$15 gift card of their choice for participating in the interview.

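### Screening asks about a current eating disorder, but the clearance list is worded for past ones, so self-reported bulimia that was never diagnosed or treated meets no listed trigger

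*Combined protocol and SAP*

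**What the plan says.** Section 3, Individual Screening Session, sets out numbered items that staff use to decide eligibility. Item 21 reads "Assess for present or history of anorexia nervosa or bulimia nervosa", so the protocol itself separates a present disorder from a past one.

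The consequences of a positive answer should be in the exclusion table of the same section, in the row on contraindications to weight loss. That row has two lists. Conditions in the first require clearance by a primary care provider. Two of its entries concern eating disorders: a history of anorexia nervosa, and "Past diagnosis of or treatment for anorexia nervosa or bulimia nervosa". Conditions in the second list lead to exclusion, and none of them is an eating disorder.

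Two rules after the screening items say what happens next. The stop rule is that "if a potential participant meets any of the exclusion criteria listed above the screening will be stopped and the participant will be deemed ineligible". The other rule holds a case as pending where, on the person's response, "it is not clear if he/she meets study criteria, and the study team member must review the case" with the study team.

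**The concern.** Item 21 collects an answer to which the written criteria attach no consequence in one situation. A person who recovered from bulimia after treatment must bring a clinician's letter. A person who reports bulimia now, but never had a diagnosis or treatment, does not have to on the wording as it stands. That is the wrong way round for a row meant to catch contraindications to weight loss.

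What is at stake is participant safety. In PeerFIT, "Participants are taught to achieve their weight loss and fitness goals by lowering calorie intake", and daily self-weighing is one of its self-monitoring strategies. The comparison arm also offers "support for self-monitoring behaviors (i.e., daily self-weighing and tracking daily steps) during the first six months of the study". Both arms thus promote behaviour on which a clinician's view would be wanted before someone with active bulimia starts.

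**Working it through.** No arithmetic beyond counting applies. The check sets item 21 against every entry that could act on its answer, all in Section 3.

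**Count of entries**

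| Place | Entries | Name a past eating disorder | Name a present eating disorder |
|---|---|---|---|
| Clearance list, weight-loss row | 4 | 2 | 0 |
| Outright exclusion list, same row | 7 | 0 | 0 |
| Medical clearance inclusion criterion (CVD risk, diabetes, PAR-Q, angina) | 4 | 0 | 0 |
| Letter triggers in screening item 22 (PAR-Q, cardiovascular disease, cardiac event, diabetes) | 4 | 0 | 0 |

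The remaining rows of the inclusion and exclusion tables do not mention eating disorders. These counts describe the wording. They do not measure how many people are affected.

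**Which people fall where**

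1. *Past bulimia, treated, now well.* Meets the entry on past diagnosis or treatment. Letter required.
2. *Current disorder, diagnosed or treated at some earlier time.* Meets the same entry, which does not require remission. Letter required.
3. *Current anorexia nervosa, never diagnosed.* Unlikely to reach this point, because the inclusion criterion is "Overweight, defined by Body Mass Index at least 25.0". The entry on a history of anorexia can also be read to include a continuing illness.
4. *Current bulimia nervosa, never diagnosed or treated.* The anorexia entry does not apply, and the other entry needs a diagnosis or treatment that this person never had. The BMI floor does not address bulimia. One exclusion, "5% or greater weight loss in 3 months prior to screening session as indicated by self-report", removes some active cases but not those with stable weight.

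For the fourth person the stop rule does not operate, because it depends on the listed criteria. The letter requirement does not operate either. What remains is the pending rule, which works only if the staff member running the session regards the case as unclear.

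**Safeguards elsewhere**

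- Section 7 foresees that signs of an eating disorder may emerge in research interviews and provides for notice to the treatment team or review with the site investigator. The visit table in Section 11 puts the baseline assessment at Visit 4 and randomization at Visit 5, so this route can act before any intervention. It sets no eligibility rule, though, and Table 1 lists no eating-disorder instrument, so detection there would be incidental.
- Section 6 (nutrient intake) provides weigh-ins at the weight management sessions and referral if a problem is suspected. Section 9 has participant concerns discussed on weekly supervision calls. Both come later.

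**The case against.** The strongest reply is that the protocol already deals with this case through judgement. The screening items do not map one to one onto the criteria: transport, upcoming surgery and scheduling conflicts are also asked about without a criterion in the same words. A present answer set against criteria worded for the past is a natural example of an unclear case, and unclear cases must go to the study team. The operational rule may also sit in the structured screening protocol or the medical condition checklist, which are mentioned but not reproduced. All participants are mental health clients whose charts are reviewed for psychiatric diagnosis.

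Much of this stands. It shows that the fourth person may well be caught. It does not show that the written criteria catch them: the route depends on individual judgement, and a disorder never diagnosed may not be in the chart. The logistical items are a weak comparison, because item 21 is a safety question whose past half already carries a written consequence.

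A reader might also infer three stronger points that the documents do not support:

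- *That no criterion acts on any present eating disorder.* A currently ill person who was ever diagnosed or treated already meets the clearance entry.
- *That every other safeguard acts only after enrolment.* The baseline interview precedes randomization, and Section 11 uses enrolled and randomized as equivalent when it describes data-sharing consent.
- *That a current disorder ought to be an outright exclusion.* The sponsor chose clearance for eating disorders in a pragmatic trial, and nothing in the documents argues for a stricter rule.

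**Conclusion.** The point holds in a narrow form and is minor. Item 21 and the clearance list do not match. The person left without a written trigger is one who self-reports a current eating disorder, in practice bulimia nervosa, that was never diagnosed or treated. Study-team review of that person is possible but not assured.

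The documents give no prevalence, so the number affected cannot be derived. It is probably very small, since it requires someone to disclose at screening a disorder that no clinician has diagnosed or treated. Sample size, power, the analysis and the treatment estimates are unaffected.

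The conclusion assumes that the exclusion table is the full statement of the criteria. If the screening protocol or checklist already sends a present answer for clearance, only the wording of this document needs aligning.

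**What to change.** Replace the second eating-disorder entry in the clearance list with wording such as *Present or past anorexia nervosa or bulimia nervosa, or diagnosis of or treatment for either*. Any positive answer to item 21 then requires primary care clearance. The same wording also covers past bulimia that was never diagnosed or treated, which the current entry misses too.

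If enrolment is complete, report instead how any answers of a present disorder were handled. The COVID-19 note under Table 1 drops physical measures only from twelve-month assessments, which suggests but does not prove that recruitment had ended by this version.

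The cost is one line of text. No new procedure is needed, because item 21 is already asked and the clearance pathway already exists. A few people may be delayed while they obtain a letter.
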